2.3 Safety evaluation

The safety and tolerability of vildagliptin 50mg bid as add-on to metformin over 5-years of treatment will be compared to placebo as add-on to metformin based on data collected during the treatment period in SAF. All analyses will use all available data collected during the entire study. In addition, key safety analyses will be performed on data obtained during Period 1 only. Patients will be analyzed according to the treatment approach they received (vildagliptin 50mg bid + metformin, placebo + metformin).

The incidence of treatment emergent adverse events (events started after the first dose of randomized study medication or events present prior to start of randomized treatment but increased in severity) will be summarized by primary system organ class, preferred term, severity and relationship to study drug. Any event captured on the database will be included in AE summary tables/listings.

In order to assess safety and tolerability of vildagliptin as compared to placebo, key safety variables (overall AEs, SAEs, AEs leading to study drug discontinuation or study drug interruption, incidence of hypoglycemia, predefined AE risks, predefined categories of liver enzyme (ALT/AST) and CPK and persistent elevations) will also be summarized by treatment approach for the SAF.

The number and percentage of run-in failures reporting any adverse events, serious adverse events or adverse events leading to study drug discontinuation will also be summarized. Note

these events will not be included in other AE outputs, as these patients will not be included in SAF.

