3.1.3 Period 2: vildagliptin/metformin combination versus vildagliptin add-on to metformin

In the case of two consecutive HbA1c measurements $\geq 7.0\%$ from two consecutive study visits during Period 1, scheduled according to [Table 6-1](#) & [Table 6-2](#), patients in both arms will receive new vildagliptin study medication packs. The investigator will contact the IRT system within 2 weeks after the receipt of the second of the two elevated HbA1c measurements. The IRT system will assign the new vildagliptin study medication packs. Patients who were randomised to the placebo arm in Period 1 will now receive vildagliptin 50mg bid. Patients who were randomised to the active vildagliptin 50mg bid arm in Period 1 will continue to receive vildagliptin 50mg bid. All patients will continue to take their metformin dose unchanged. Period 2 will remain masked to the patient and both patients and investigators will remain masked to the treatment allocation in Period 1.

Any anti-diabetic medication other than the study regimen is not allowed during Period 2, except if the patient had temporarily reduced/interrupted the treatment regimen due to AEs or untoward events that require temporary dose adjustment/interruption (see [Section 5.5.5](#)).

If, during Period 2, therapy intensification is required in accordance with the local guidelines, the patient will enter Period 3.

The duration of Period 2 may differ between patients. End of Period 2 is considered when insulin treatment is initiated, or alternatively when the patient is discontinued because insulin treatment is not initiated in Period 3 (see [Section 3.1.4](#)).

[figure not shown]

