5.2 Treatment arms

Patients will be assigned in a ratio of 1:1 to one of two treatment arms:

- Metformin up to 1000mg bid plus vildagliptin 50mg bid (Period 1). In Period 2 and 3 these patients will receive metformin up to 1000mg bid plus vildagliptin 50mg bid.
- Metformin up to 1000mg bid plus vildagliptin placebo 50mg bid (Period 1). In Period 2 and 3 these patients will receive metformin up to 1000mg bid plus vildagliptin 50mg bid.

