9.5.3 Safety variables

[figure not shown]
The safety and tolerability of vildagliptin 50mg bid as add-on to metformin over 5-years of treatment will be compared to placebo as add-on to metformin based on data collected during the randomised treatment period in SAF set.

The assessment of safety will be based mainly on the frequency of treatment emergent AEs (including overall AEs), SAEs, death, AEs leading to study discontinuation or study drug interruption & pre-specified AE risks on the number of post BL laboratory values that fall outside of pre-determined ranges and on the frequency and severity of hypoglycemic events during the randomised treatment period. Summaries for safety assessment will be presented for the SAF set. Unless specified otherwise, comparison will be made to BL, which will be the measurement taken at Visit 3, or the sample obtained at an earlier visit (scheduled or unscheduled) which was closest to Day 1 if Day 1 measurement is missing.

AEs will be summarised by presenting, for each treatment group (vildagliptin 50mg bid + metformin, placebo + metformin), the number and percentage of patients having any AE, having an AE in each primary SOC and having each individual AE. Any other information collected (e.g. severity or relatedness to study medication) will be presented as appropriate.

[figure not shown]
Laboratory data will be summarised by presenting summary statistics of raw data and change from BL values (means, medians, standard deviations, ranges) and by presenting the number and percentage of patients having notable lab values or having endpoint change from BL meeting pre-specified percent change criteria. The identification of notable values will be based on the pre-specified criteria provided in the investigator binder (will also be included in the analysis plan). The predefined categories of liver enzyme (ALT/AST) and CPK elevations and persistent elevations will be summarised by treatment.

Hypoglycemia events will be included in all AE summaries. In addition, events will be characterised by event profile, such as ability to self-treat, self monitoring of plasma glucose level, precipitating event, time from last meal, time from last dose, and time of the day.

[figure not shown]
Data from other tests (e.g. vital signs including [redacted], ECGs) will be summarised as appropriate, incidences of notable values will be presented in the tables and notable values will be flagged in the listings.

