2.1.6 Study medication

The study consists of three treatment periods.

In Period 1 patients will be randomized to metformin + vildagliptin 50mg bid, or metformin + placebo. If initial treatment fails to maintain HbA1c < 7.0%, confirmed at two consecutive scheduled study visits (after remapping in [section 1.3.3](#) has been applied), starting from Visit 4 (Week 13), then vildagliptin will be added to metformin in the metformin-only arm in Period 2. The Period 1 end date is defined as the date of the second of the two consecutive scheduled study visits, i.e. the initial treatment failure date. The Period 2 start date is defined as the next day.

In Period 3, insulin is considered based on local guidelines. Both patients and investigators will remain masked to the treatment allocation in Period 1, and the study will compare the two different treatment approaches. The Period 3 start date is defined as the date of insulin initiation. The Period 2 end date is defined as the previous day.

Treatments are referred to as ‘Treatment approach’ throughout this analysis plan to acknowledge that patients are not on the same treatment for the duration of the study. When summaries are detailed for the ‘Treatment Period’, they will include data from Periods 1, 2 and 3, unless specified otherwise.

The duration of exposure to study medication (in months) during the treatment period will be computed for all patients using the algorithm outlined in [Section 1.4](#) and summarized by treatment approach for the RAN both descriptively (i.e., mean, standard deviation, median, minimum and maximum) and by 3 - monthly intervals (0 - < 3 months, 3 - < 6 months, ..., ≥ 60 months).

The study Period 1 duration (in months) will be also similarly summarized for the RAN. The study Period 1 duration is defined as (initial treatment failure date – treatment start date + 1)/30.4375 for patients who entered study Period 2. The study Period 1 duration is the same as overall study duration for patients who did not enter into Period 2.

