The study period from treatment start to the end of Period 2 will be computed for all patients who initiate insulin in Period 3 and for patients discontinuing the study in Period 2 due to being unable or unwilling to initiate insulin for treatment intensification in Period 3. The duration will be defined as (initiation date of insulin – treatment start date)/30.4375 for patients who initiate insulin, and (last study drug date – treatment start date + 1)/30.4375 for patients who do not enter Period 3.

Total subject year exposure (SYE) will also be summarized by treatment approach for the RAN. SYE (years) for each treatment will be calculated as (duration of exposure in days, disregarding any treatment interruptions, for all subjects in that treatment approach) / 365.25. For patients who did not take any study medication, the exposure is set to zero. This summary will be repeated on Period 1 data only, and also on Vildagliptin exposure only.

Study medication information will be listed for the RAN, including information about vildagliptin, placebo, metformin and insulin use.

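### Whole-study safety tables are described as vildagliptin versus placebo over 5 years, although failed placebo patients receive vildagliptin; Period 1 should be named as the drug comparison

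*SAP*

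**What the plan says.** Protocol 9.5.3 states the aim: "The safety and tolerability of vildagliptin 50mg bid as add-on to metformin over 5-years of treatment will be compared to placebo". SAP 2.3 repeats it, saying that vildagliptin "will be compared to placebo as add-on to metformin based on data collected during the treatment period in SAF", and sets the data scope: "All analyses will use all available data collected during the entire study". The next sentence adds a restricted version: "In addition, key safety analyses will be performed on data obtained during Period 1 only". Protocol 9.5.3 closes with the same two statements. The two groups are labelled vildagliptin 50mg bid + metformin and placebo + metformin. The text of SAP 2.3 quoted here is the same in V3.0 and Addendum 1.

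The design changes the placebo group's treatment at failure. Protocol 3.1.3 says: "Patients who were randomised to the placebo arm in Period 1 will now receive vildagliptin 50mg bid". Protocol 5.2 says of the placebo arm: "In Period 2 and 3 these patients will receive metformin up to 1000mg bid plus vildagliptin 50mg bid".

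The SAP recognises this. SAP 2.1.6 calls the arms treatment approaches "to acknowledge that patients are not on the same treatment for the duration of the study", and defines the treatment period as Periods 1, 2 and 3 unless stated otherwise. It also plans a total of subject-years by arm: "This summary will be repeated on Period 1 data only, and also on Vildagliptin exposure only".

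**The concern.** The stated contrast is vildagliptin against placebo for 5 years. The design provides that contrast only until a placebo patient fails. After that both arms take vildagliptin, and an event caused by the drug in a former placebo patient counts against placebo in any whole-study table. Differences caused by the drug then shrink, which is the unsafe direction for a safety conclusion.

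This matters because Amendment 3 presents the trial as a source of long-term safety data, and the predefined risks in SAP 1.6 include drug-induced liver injury and cancers. A reader who takes the whole-study table at its label would understate any excess on vildagliptin.

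**Working it through.** The documents give no expected number of switchers, adverse event rate or safety power, so there is no stated figure to reproduce. The size of the problem can be derived from the plan's efficacy assumptions.

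**Inputs**
- Failure in the metformin arm: 7.1% a year (protocol 9.6), used as a rate of 0.071, or as -ln(1 - 0.071) = 0.0736.
- Initial failures: 10% in each arm after 13 weeks (protocol 9.6), placed at t0 = 0.25 years, or at 0.5 years because the earliest confirming visit is Week 26.
- Hazard ratio for failure: 0.75 (protocol 9.6).
- Dropout: 11% a year (protocol 9.6; SAP 2.7, Addendum 1) or about 4% (SAP 2.7, V3.0). Zero is added as a bound. Each is used as a constant rate d.
- True adverse event rate ratios of 1.5 and 2.0: my assumption, not in the documents.

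**Step 1: placebo-arm time on vildagliptin.** With failure rate λ:

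Total time = (1 - e^(-5d))/d

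Period 1 time = (1 - e^(-d·t0))/d + 0.9·e^(-d·t0)·(1 - e^(-(λ+d)(5-t0)))/(λ+d)

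For d = 0.04, λ = 0.071, t0 = 0.25:
- Total = (1 - e^(-0.20))/0.04 = 4.53 years.
- Period 1 = 0.249 + 0.9 × 0.990 × (1 - e^(-0.527))/0.111 = 0.249 + 3.289 = 3.54 years.
- Share on vildagliptin s = 1 - 3.54/4.53 = 0.219.
- Proportion switching = 0.990 × [0.1 + 0.9 × 0.071 × 3.692] = 0.333, where 3.692 = (1 - e^(-0.527))/0.111.

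Across both values of λ and t0:

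| Dropout per year | Placebo patients switching | Share of placebo-arm time on vildagliptin |
|---|---|---|
| 0 | 34.6-36.6% | 20.7-22.8% |
| 4% | 32.0-34.0% | 20.1-22.3% |
| 11% | 28.1-30.2% | 19.2-21.4% |

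This counts time from confirmed failure. New packs come later (protocol 3.1.3), so the share is slightly high. Each two weeks of delay moves about 0.333 × 2/52 = 0.013 of 4.53 years, or 0.3 percentage points.

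**Step 2: effect on a whole-study rate ratio.** With constant rates, apparent ratio = RR/((1 - s) + s·RR).
- RR 1.5: 1.5/(0.81 + 0.19 × 1.5) = 1.37; 1.5/(0.77 + 0.23 × 1.5) = 1.35.
- RR 2.0: 2/(0.81 + 0.38) = 1.68; 2/(0.77 + 0.46) = 1.63.
- The rate difference keeps 1 - s, or 77-81%, of its size.

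In Period 1, s = 0 and this dilution disappears.

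**Step 3: Period 1 length by arm.** With λ multiplied by 0.75, the same formula gives 3.67 years on vildagliptin against 3.54 on placebo at 4% dropout (ratio 1.04), and 3.14 against 3.04 at 11% (1.03). Across the variants Period 1 is about 3-4% longer on vildagliptin.

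**Step 4: which outputs have a Period 1 version in the SAP**

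| Output | Period 1 or by-period version |
|---|---|
| AEs by organ class and preferred term (2.3.1) | Stated |
| Overall counts of drug-related and severe AEs (2.3.1) | Stated |
| Deaths, SAEs, discontinuations, interruptions, predefined risks (2.3.1.1) | Stated |
| Notable hematology, biochemistry, vital signs (2.3.2, 2.3.3) | Stated |
| Hypoglycemia summary and chi-square test (2.3.5) | Stated; the test is Period 1 only |
| Text Table of AEs at 2% or more (2.3.1) | Not stated |
| Detailed related-AE, maximum-severity and SMQ tables (2.3.1) | Not stated |
| Hepatic enzyme and CPK elevations (2.3.2.2) | Only by inference from the key safety variables listed in 2.3 |

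The AE tables give percentages of patients. None is stated to use the subject-years from SAP 2.1.6.

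**The case against.** The strongest reply is that the SAP largely handles the switch. AEs, deaths, SAEs, discontinuations, interruptions and predefined risks are all shown by period, the hypoglycemia test is confined to Period 1, and the arms are deliberately called treatment approaches. A whole-study summary by assigned strategy is a legitimate long-term description. Nothing in the SAP says that the whole-study tables carry the safety conclusion.

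Most of this stands, and it rules out two stronger inferences. A reader might infer that Period 1 results are limited to a narrow set of key variables; Step 4 shows that they are not. A reader might also infer that the trial's safety conclusion as a whole rests on diluted data; the documents do not support that, because the undiluted tables for the main event categories are planned.

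The arithmetic also has limits. It concerns person-time rates with constant hazards, whereas the tables show percentages of patients with an event. Early-onset events would be diluted less. Insulin in Period 3 can shift whole-study hypoglycemia in either direction.

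The reply does not remove three gaps. The opening sentences of SAP 2.3 and protocol 9.5.3 still promise a 5-year placebo contrast, with whole-study data as the default and Period 1 as an addition. Several tables have no stated Period 1 version. No exposure-adjusted event rates are specified.

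**Conclusion.** The concern holds in a limited form. The whole-study tables compare starting with the combination against starting with metformin and adding vildagliptin at failure; they do not compare vildagliptin with placebo for 5 years. About 28-37% of placebo patients would switch (28-34% at the two dropout rates in the documents), and 19-23% of that arm's time would be on vildagliptin. For an assumed true rate ratio of 1.5 or 2.0, the whole-study ratio would be about 1.35-1.37 or 1.63-1.68. These figures rest on the plan's failure and dropout assumptions, constant event rates, and a risk that applies only while on the drug. They illustrate size and do not predict the planned percentages.

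The dilution is moderate and confined to whole-study outputs. It is worth correcting because the remedy is cheap and the bias runs toward no difference.

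**What to change.** In SAP 2.3 and protocol 9.5.3:

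1. Name Period 1 as the vildagliptin-versus-placebo safety comparison.
2. State that it covers the Text Table of AEs at 2% or more, the detailed related-AE, maximum-severity and SMQ tables, and the hepatic enzyme and CPK elevations.
3. Add rates per 100 subject-years to the main AE, SAE and predefined-risk tables, using the subject-years already planned in SAP 2.1.6.
4. Keep the whole-study tables, labelled as a comparison of treatment approaches, and reword the opening sentences to match.
5. If rates on and off vildagliptin are shown, mark them as non-randomised and supportive only. All time after failure is on vildagliptin, so that contrast mixes drug with disease progression, time in study and insulin.

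The cost is SAP and protocol wording plus extra table columns, with no new data collection. The main limitation is that Period 1 ends at treatment failure, so follow-up depends on outcome and differs slightly by arm. Rates adjust for the difference in length but not for the selection, and the report should say so.

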2.3.1 Overall experience of adverse events (AEs)

The number and percentage of patients reporting any adverse event during the treatment period of the study will be summarized by primary system organ class, preferred term and treatment approach overall (including study periods 1, 2 and 3) and by study period. Percentages will be based on the number of patients in the SAF per treatment approach and study period. An AE will be assigned to a period if its start date is after or on the start date but not later than the end date of that period. All AEs will be assigned to a specific study period – if it is not possible to assign an AE into a specific study period of the patient based on the AE start date, then the event will be assigned to the last study period started by the patient. This will ensure that all AEs will be categorized to a specific study period

The most common adverse events reported ($\geq 2\%$ in any group) during the treatment period of the study will be presented in descending frequency starting from the most common event in a Text Table. A complete table of all events reported in descending frequency will be prepared..

Adverse events that were suspected to be related to study drug will be summarized. Note that if the relationship to study drug is missing for any adverse event, then that adverse event will be assumed to be related to study drug.

The maximum severity of all adverse events during the treatment period of the study will be summarized. Note that if the severity is missing for any adverse event, then that adverse event will be assumed to be severe.

An overall summary of the number and percentage of patients with drug-related AEs, severe AEs, AEs with outcome of death, SAEs and adverse events leading to permanent discontinuation of treatment will be presented by study period and treatment approach.

The number and percentage of patients reporting any adverse event during the treatment period of the study will be summarized by standardized MedDRA query (SMQ) level and treatment approach as well.

In addition, the number and percentage of patients reporting any adverse event during the treatment period will also be summarized by primary system organ class, preferred term, treatment approach and age group (as defined in section 2.1.5)) overall and by treatment period..

Note that there will be no AE adjudication for this study.

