3.1.2 Period 1: vildagliptin/metformin combination versus metformin

At Visit 3, patients will be randomised 1:1 to one of the following study regimens:

- Metformin up to 1000mg bid plus vildagliptin 50mg bid or
 - Metformin up to 1000mg bid plus matching placebo bid.
- 

During the first 4 weeks of Period 1 the metformin dose can be adjusted (increased or decreased, but not below 1000mg daily or above 2000mg). An unscheduled visit can be performed in order to adjust the metformin dose if deemed necessary. The objective is to optimise metformin dose to 2000mg daily or to the maximum tolerated dose. Patients who are unable to tolerate a total daily dose of 1000mg metformin will be discontinued. The metformin dose at week 4 post-randomisation and the vildagliptin 50mg bid or matching placebo bid dose should remain unchanged throughout the duration of the study, except for AEs or untoward events that may require dose reduction or interruption (see [Section 5.5.5](#)).

Any anti-diabetic medication other than the study drug regimen is not allowed during Period 1, except if the patient had temporarily reduced/interrupted the treatment regimen due to AEs or untoward events that require temporary dose adjustments. In such cases dose adjustments or interruptions of the study drug are permitted (see [Section 5.5.5](#)). Patients who, during Period 1, take anti-diabetic medication other than the study drug regimen (except for AEs or untoward events that require temporary dose adjustments, see [Section 5.5.5](#)) will be discontinued from the study.

The duration of Period 1 may differ between patients depending on the time when the second of two HbA1c measurements taken at two consecutive visits after randomisation ([Table 6-1](#) & [Table 6-2](#)) confirms HbA1c $\geq 7.0\%$.

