9.6 Sample size calculation

A total sample size of 1000 randomised patients per treatment arm (in 1:1 allocation ratio to vildagliptin + metformin and metformin monotherapy) is planned.

Power calculation for the time-to-treatment failure variable

The sample size calculation assumes that all randomised patients are to be followed up for 5 years unless patients dropped out from the study for various reasons (lack of efficacy, AEs,

abnormal labs, lost to follow-up etc.), and that the yearly dropout rate is 11% (estimate based on ADOPT data (Kahn S et al, 2006)).

The existing vildagliptin study data suggest that approximately 10% of vildagliptin patients will have an HbA1c >7.0% after the first 3 months of the study (initial response phase), since those patients who are randomised with an HbA1c measurement above the failure threshold (7.0%) may never have an HbA1c measurement below the required threshold during the study and will therefore be counted as failures during the first 13 weeks. A similar proportion is assumed for the comparator arm. Hence it is expected that the difference in failure rate is likely to be small early in the study, but will diverge as the study progresses. The power calculations have been adjusted to take this assumption into account using statistical simulations.

The simulations showed that assuming an annual initial treatment failure rate of 7.1% in the metformin monotherapy arm (estimated based on ADOPT data), incorporating a 10% initial failure rate after 13 weeks in each treatment arm (due to some patients with BL HbA1c $\geq 7.0\%$), 1000 patients per treatment arm would be sufficient to detect a hazard-ratio of 0.75 between vildagliptin + metformin and metformin alone (corresponding to a risk reduction rate of 25% in vildagliptin + metformin group *versus* metformin alone) with approximate 66% power and a 1-sided significance level of 0.025 (corresponding to a 2-sided test at 0.05).

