A listing of hypoglycemic events and asymptomatic low blood glucose events will be presented by treatment approach and patient number.

[figure not shown]
Note: As defined in [Table 1-1](#), for patients who are able to initiate self-treatment (where necessary) symptoms suggestive of hypoglycemia which are not confirmed by glucose measurements will be recorded in the Glycemia diary eCRF. Since these are not confirmed hypoglycemia events, these symptoms will not be reported in the hypoglycemia summary tables and listings, these symptoms will appear only in the AE tables and listings. For patients unable to initiate self-treatment (where necessary) symptoms suggestive of hypoglycemia that were not confirmed by glucose measurements will be classed as suspected hypoglycemic events and will therefore be reported in the hypoglycemia summary tables and listings, as well as the AE listings.

[figure not shown]
Note: Self-monitoring glucose can be recorded in the database as either plasma or whole blood. However, only plasma glucose will be reported in the tables and listings. Thus blood glucose values will be converted into plasma glucose equivalent, which can be done by multiplying a conversion factor of 1.12, i.e., plasma glucose = blood glucose × 1.12.

The incidence of hypoglycemia and severe hypoglycemia during Period 1 will be compared for the SAF using a chi-square test between the two treatment approaches for all patients provided that the incidence such these events is more than 5 in each treatment approach.

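### Period 1 adverse events and hypoglycemia are summarised as crude percentages although Period 1 ends at the primary event, which builds in a small excess for the combination arm

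*SAP*

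**What the plan says.** Period 1 has no fixed length. Protocol 3.1.2 states: "The duration of Period 1 may differ between patients depending on the time when the second of two HbA1c measurements" confirms failure. SAP 2.1.6 gives the matching rule: "The Period 1 end date is defined as the date of the second of the two consecutive scheduled study visits". SAP 2.2.2.1 treats that same date as the primary event.

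Placebo control stops there. Protocol 3.1.3: "Patients who were randomised to the placebo arm in Period 1 will now receive vildagliptin 50mg bid".

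SAP 2.3 bases safety on all data from the whole study, and then adds: "In addition, key safety analyses will be performed on data obtained during Period 1 only". For the by-period adverse event tables, SAP 2.3.1 sets the denominator: "Percentages will be based on the number of patients in the SAF per treatment approach and study period". SAP 2.3.1.1 gives deaths, SAEs, discontinuations and predefined risks in the same way, as numbers and percentages by period and arm.

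SAP 2.3.5 contains the only formal between-arm safety test that can be seen: "The incidence of hypoglycemia and severe hypoglycemia during Period 1 will be compared for the SAF using a chi-square test". It is run only if incidence exceeds 5 in each arm.

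Subject-years of exposure are calculated in SAP 2.1.6, for the randomised set: "This summary will be repeated on Period 1 data only, and also on Vildagliptin exposure only". No visible safety table uses them. The text is the same on these points in SAP V3.0 and Addendum 1.

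**The concern.** The length of the observation window is itself the efficacy outcome. If the primary hypothesis is true, combination patients leave Period 1 later and have more time in which to report a first event. A percentage of patients, or a chi-square test on it, cannot separate a higher risk from a longer period of observation. The distortion points one way when the drug works: against the combination arm. It grows with the treatment effect and the failure rate.

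What is at stake is the reading of the one part of the safety data in which vildagliptin can be set against placebo, and the p-value for Period 1 hypoglycemia.

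**Working it through.** **The plan's own figure.** The safety sections give no number to reproduce, but the sample size section gives a failure model, and I checked that first. A log-rank simulation (4,000 runs, 1,000 per arm) had exactly 10% of each arm failing at week 13. Other failures were exponential at 7.1% per year with hazard ratio 0.75, dropout was exponential, and follow-up was 5 years on the 13-week visit grid. Power was 65.2% at 11% dropout (Protocol 9.6 states about 66%) and 76.7% at 4% dropout (SAP V3.0, 2.7 states about 75%). The failure model is therefore a fair basis for what follows.

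**Inputs from the documents.** Sample size (Protocol 9.6): "A total sample size of 1000 randomised patients per treatment arm". Metformin-arm failure 7.1% per year; 10% early failure in both arms; hazard ratio 0.75; 5 years of follow-up; yearly dropout 11% (Protocol 9.6, Addendum 1) or about 4% (SAP V3.0).

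**Assumptions.** Early failures leave Period 1 at 0.5 year, because two consecutive visits starting at week 13 cannot confirm failure before week 26. The event hazard e is constant and equal in both arms. The documents give no value for it, so I use 0.005, 0.02 and 0.1 per patient-year. The chi-square is taken as two-sided at 5%, since SAP 2.3.5 gives no level.

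**Hazards.** Failure: h = −ln(0.929) = 0.0736 for metformin, and 0.75 × 0.0736 = 0.0552 for the combination. Dropout: d = −ln(0.96) = 0.0408 or −ln(0.89) = 0.1165.

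**Mean Period 1 time.** With A(r, T) = (1 − exp(−rT))/r, mean time = 0.1 × A(d, 0.5) + 0.9 × A(h + d, 5).

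- 4% dropout, metformin: 0.1 × 0.495 + 0.9 × 3.807 = 3.476 years. Combination: 0.1 × 0.495 + 0.9 × 3.971 = 3.623 years. Ratio 1.042.
- 11% dropout, metformin: 0.1 × 0.486 + 0.9 × 3.227 = 2.952 years. Combination: 0.1 × 0.486 + 0.9 × 3.355 = 3.068 years. Ratio 1.039.

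Putting the early failures at week 13 and starting the later hazard there gives 1.038 and 1.035, so the answer does not hang on that choice.

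**Crude percentage under equal hazards.** p = e × [0.1 × A(d + e, 0.5) + 0.9 × A(h + d + e, 5)]. The chance of a false finding that vildagliptin is higher is 1 − Φ(1.96 − difference/SE), where SE² = [p₁(1 − p₁) + p₂(1 − p₂)]/1000.

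| Dropout | e per year | Metformin | Combination | Excess (points) | SE (points) | False finding (nominal 2.5%) |
|---|---|---|---|---|---|---|
| 4% | 0.005 | 1.72% | 1.79% | 0.07 | 0.59 | 3.3% |
| 4% | 0.02 | 6.65% | 6.93% | 0.28 | 1.13 | 4.3% |
| 4% | 0.1 | 28.09% | 29.16% | 1.08 | 2.02 | 7.7% |
| 11% | 0.005 | 1.46% | 1.52% | 0.06 | 0.54 | 3.2% |
| 11% | 0.02 | 5.67% | 5.89% | 0.22 | 1.04 | 4.0% |
| 11% | 0.1 | 24.22% | 25.08% | 0.86 | 1.93 | 6.5% |

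**With person-time.** In simulation at 4% dropout and e = 0.1, with the week-13 timing, the crude chi-square gave a false finding in 7.3% of trials. Patients with an event per person-year to first event gave a mean rate ratio of 1.00 and a false finding in 2.6%.

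**Sensitivity (assumed, not in the plan).** A hazard ratio of 0.6 gives person-time ratios of 1.069 (4% dropout) and 1.064 (11%). A hazard ratio of 0.5 gives 1.087 and 1.081.

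**The case against.** The strongest reply is that the effect is small and the plan already shows part of it. At an event rate of 0.02 per year the artefact is about 0.28/1.13 = 0.25 of a standard error. Protocol 3.4 and 3.6 lead one to expect little hypoglycemia on either regimen, so the one formal test probably sits at the low end of the table. The other tables are descriptive. The bias overstates harm and does not hide it. Period 1 duration and subject-years are tabulated by arm, so a reader can see the imbalance. All of this stands and limits the weight of the point. The exposure tables do not solve it: they use the randomised set, are not tied to the event tables, and do not stop the clock at the first event.

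A second reply concerns the remedy. Failure cannot be confirmed before week 26, so for early-onset events the crude percentages are nearly unbiased. Dividing by all Period 1 time would then give a false ratio of about 1/1.04 = 0.96 in the combination's favour. Leaving Period 1 also depends on HbA1c, so censoring there may be informative for hypoglycemia. Both points stand. They argue for rates beside the percentages and not in their place.

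A reader might infer three stronger things.

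- That the whole safety assessment rests on Period 1. SAP 2.3 and Protocol 9.5.3 use all study data first and Period 1 in addition. The overall tables are not cut off at failure, though they do mix vildagliptin into both arms.
- That the Period 2 tables share the same bias. The documents give no figures for Period 2 time by arm. Those patients are also selected after randomisation by having failed, which exposure adjustment cannot repair.
- That the distortion is large. That needs hazard ratios below 0.75 or failure rates above 7.1%, neither of which the plan states.

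**Conclusion.** The concern holds as a modest one. Period 1 length depends on treatment through the primary event, and the Period 1 event percentages and hypoglycemia chi-square ignore it. On the planning inputs the combination arm has about 4% more person-time. With equal hazards this gives a spurious excess of about 0.06 to 0.28 points for rare events and about 1 point at 0.1 per year, where the one-sided false-finding rate is about 6.5% to 7.7% instead of 2.5%.

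These figures rest on the plan's failure model, on assumed event rates, and on constant, equal event hazards; a true difference in rates would add to or offset the artefact. Redacted safety sections may contain more and are not counted as missing.

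**What to change.** In SAP 2.3.1, 2.3.1.1 and 2.3.5, for the key Period 1 safety variables (AEs, SAEs, predefined risks, hypoglycemia), add in the safety set, beside the percentages, the number of patients with an event per 100 subject-years to first event or end of Period 1. Give the between-arm ratio or difference with a 95% confidence interval. Accompany the hypoglycemia chi-square with a time-to-first-event comparison censored at the end of Period 1, and interpret the chi-square in its light.

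State the limits in the text: a constant-rate summary can mislead for early-onset events, which is why the percentages stay, and censoring at the end of Period 1 depends on glycemia. If the addition is made after unblinding, label it post hoc.

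The cost is SAP wording, extra table columns and one further analysis. Period dates and subject-years are already derived; they need to be rebuilt on the safety set and stopped at the first event.
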